### **Evaluation of the Practice Facilitation Intervention: Implementation and Clinical Outcomes.**

Aim 3 implementation and clinical-specific outcomes were derived guided by the RE-AIM (Reach, Effectiveness, Adoption, Implementation, and Maintenance) evaluative framework, often used to guide implementation evaluations. RE-AIM will be assessed using EHR data pulled from VA's Corporate Data Warehouse (CDW). The data pull will include data from January 1, 2019 – December 31, 2023, to evaluate these outcomes, which includes the pre-intervention period, the active facilitation intervention period, and the post-facilitation intervention period (i.e., 3-, 6-, and 12-months after active implementation). RE-AIM constructs are defined as follows:

**Reach** of alcohol-related care will be assessed at the patient level using EHR data, pulled from VA's CDW. **Reach** outcomes will be expressed as a rate, with the

denominator (for all outcomes) defined as all Veterans with a visit to the Pittsburgh VA primary care clinic during the practice facilitation intervention. The numerator for each Reach outcome is as follows: the number of Veterans who screened positive for unhealthy alcohol use (AUDIT-C  $\geq$  5) AND had any documented brief intervention, encounters with primary care-mental health integration (PC-MHI), encounters with PACT/ Whole Health clinical pharmacists, specialty addictions treatment (inpatient and outpatient clinic visits for substance use disorder treatment encounters with an accompanying AUD diagnosis), or pharmacotherapy for AUD (any filled prescription for FDA-approved medications: acamprosate, disulfiram, or oral/injectable naltrexone or non-FDA approved effective medications: gabapentin, baclofen, or topiramate) in the 30 days following a positive screen. Denominators will also be derived to represent specific subpopulations (e.g., women, Black and Hispanic Veterans). Rates at the start of the practice facilitation intervention and at 3- and 6-months post intervention will be calculated to examine change in Reach outcomes over time.

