**Adoption** is identified as the percentage of providers from the PC clinic who deliver alcohol-related care when a Veteran screens positive for unhealthy alcohol use. Specifically, we will use data available in the EHR to examine delivery of brief interventions, consults placed to PC-MHI/clinical pharmacists or specialty addictions treatment and providing pharmacotherapy for AUDs at the provider and clinic level. Rates of alcohol-related care pre-intervention (2019-2022), during the course of the practice facilitation intervention (July 2022-December 2022), after the intervention (e.g., 3- and 6-months post intervention (Jan 1, 2023-March 31, 2023, and Jan 1, 2023-June 30, 2023 respectively) will be used to measure whether adoption rates of alcohol-related care increased over time.

**Maintenance** is defined as the extent to which evidence-based alcohol care becomes routine and part of the PC culture (care sustained over time). Reach and Adoption outcomes using EHR data will be assessed at 12-months post intervention (Jan 1, 2023-Dec. 31, 2023) to examine whether high-quality alcohol care was sustained.

**Effectiveness** is defined as the prevalence of unhealthy alcohol use at 12-months post-intervention (Jan 1, 2023-Dec. 31, 2023) as measured by AUDIT-C scores pulled from the EHR. This variable will also be expressed as a rate with the denominator defined as all Veterans with a visit to PC during the practice facilitation intervention (same as for Reach outcomes). The numerator will be the number of Veterans with an encounter in PC who screened positive for unhealthy alcohol use (AUDIT-C  $\geq$  5) at 12-months post facilitation intervention. While it is unlikely that a pilot study will have a measurable

impact on clinical outcomes, measuring effectiveness will serve as pilot data for a larger trial.

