#### **5.7 Data Analysis**

**Implementation Outcomes:** Reach outcomes will be reported descriptively (e.g., percentage of patients with an AUDIT-C  $\geq 5$  who were offered a BI or pharmacotherapy for AUD) and compared pre- (2019-2022) and post-implementation (at 3- and 6-months) to see whether Reach of alcohol care increased over time. Adoption outcomes via EHR will be descriptive, and include percentages, frequencies, and means (SD) of alcohol-related care by provider and clinic to understand whether Adoption of high-quality alcohol-related care increased over time. Descriptives will be examined and compared at the start of Active Implementation and at 3- and 6-months post Active Implementation. Reach and Adoption rates will again be examined at 12-months post Active Implementation and compared to rates at 3- and 6-months to see if high-quality alcohol-related care was sustained (Maintenance). **Effectiveness outcomes:** Effectiveness will be assessed via a time-series analysis, where the intervention site will serve as its own control, and we will investigate whether Veterans' with an encounter in Pittsburgh VA Primary Care during the implementation intervention reduced their drinking 12-months post intervention using AUDIT-C scores in the EHR. Time-series analysis was chosen because historical trend is accounted for in the analytic model, results can be displayed graphically, and the size of the effect can be estimated at different times post

intervention. The outcome (AUDIT-C scores) will be modeled using a regression model with an indicator for practice facilitation (pre- vs. post-), a continuous term for time (days since practice facilitation dissemination) and the interaction between the two. The indicator variable will assess immediate changes in AUDIT-C scores post implementation intervention, while the interaction term will assess if there is a change in the slope of AUDIT-C scores pre- and intervention at 12-months. While there is controversy over whether pilot studies should assess clinical efficacy or effectiveness, we decided to examine it here as a training opportunity and as preparation for a possible hybrid effectiveness-implementation Merit trial investigating practice facilitation as a way to improve alcohol-related care on a larger scale.

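### The Effectiveness analysis does not separate the AUDIT-C that triggers care from a later score that could reflect it, which mainly shifts a reduction from the level term into the slope and dilutes the 2023 prevalence

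*Combined protocol and SAP*

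**What the plan says.** Section 5.1 places care after the screen. Reach counts brief intervention, referral encounters or medication "in the 30 days following a positive screen". Adoption is the "percentage of providers from the PC clinic who deliver alcohol-related care when a Veteran screens positive".

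Effectiveness is the "prevalence of unhealthy alcohol use at 12-months post-intervention (Jan 1, 2023-Dec. 31, 2023) as measured by AUDIT-C scores pulled from the EHR". On the numerator, the plan states: "The numerator will be the number of Veterans with an encounter in PC who screened positive for unhealthy alcohol use" (AUDIT-C of 5 or more). The denominator is all Veterans with a primary care visit during facilitation. The 12-month Reach and Adoption assessments use the same January–December 2023 window.

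Section 5.7 asks whether Veterans with a primary care encounter "during the implementation intervention reduced their drinking 12-months post intervention using AUDIT-C scores in the EHR". The regression has "an indicator for practice facilitation (pre- vs. post-), a continuous term for time (days since practice facilitation dissemination") and their interaction. The indicator is to show the immediate change and the interaction the change in slope. Facilitation ran "during the course of the practice facilitation intervention (July 2022-December 2022").

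The documents do not state how often AUDIT-C is given, whether *post* begins in July 2022 or January 2023, or whether a Veteran's first screen after facilitation began is a baseline or an outcome.

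**The concern.** A first positive AUDIT-C in, say, March 2023 has two roles. It opens the 30-day window in which care is counted, and it enters the *post* segment and the 2023 prevalence as an outcome. It cannot show the result of the care that it starts. If many *post* scores are of this kind, the average pre-to-post difference is pulled toward zero. Second screens arrive only later, so an immediate benefit would appear as a gradual one. The term that section 5.7 reads as the immediate change could even point the wrong way. These estimates are meant to inform a larger trial, so a distorted level, slope or prevalence would carry into its planning.

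**Working it through.** The plan states no effect size, power or sample size for this outcome, so there is no figure to reproduce.

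**Inputs from the documents.** Facilitation ran July–December 2022; data end on 31 December 2023; care is counted within 30 days of a positive screen; the cohort is Veterans with a visit during facilitation; the model is indicator, time and interaction.

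**Assumptions.** The screening interval is taken as 11–12 months, with 6 months as the alternative. *Post* starts in July 2022 or January 2023. The true effect is −1 on every score after a Veteran's first screen on or after 1 July 2022, and 0 on that first screen. The pre-period is flat, and time zero is the start of *post*.

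**Hand check, strict annual clock with evenly spread due dates.** First screens fill July 2022–June 2023, and second screens start in July 2023. Let the *post* segment last L years, with second screens starting s years into it.

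- First-screen share = s/L
- Mean shift = −(L−s)/L
- Fitted slope b = −6s(L−s)/L³
- Indicator a = mean shift − bL/2
- Effect at end of 2023 = a + bL

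*Post* from January 2023 (L = 1, s = 0.5): share 50%; mean −0.50; b = −6 × 0.25 = −1.50 per year; a = −0.50 + 0.75 = +0.25; end = 0.25 − 1.50 = −1.25.

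*Post* from July 2022 (L = 1.5, s = 1): share 1/1.5 = 67%; mean −0.33; b = −6 × 0.5/3.375 = −0.89 per year; a = −0.33 + 0.67 = +0.33; end = 0.33 − 1.33 = −1.00.

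**Simulated screening histories, same model fitted by least squares.** With irregular visits, visits are random and a screen is given at the first visit after it falls due.

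| Screening and visits (assumed) | *Post* from | First-screen share | Indicator | Mid-segment effect | Effect at 31 Dec 2023 |
|---|---|---|---|---|---|
| 12 months, one regular visit a year in Jul–Dec | Jul 2022 | 50% | +0.19 | −0.50 | −1.19 |
| same | Jan 2023 | 0% | −1.00 | −1.00 | −1.00 |
| 11–12 months, irregular visits | Jul 2022 | 72–86% | +0.14 to +0.24 | −0.21 to −0.28 | −0.59 to −0.85 |
| same | Jan 2023 | 49–68% | +0.20 to +0.31 | −0.25 to −0.42 | −0.77 to −1.08 |
| 6 months, fixed clock | Jul 2022 | 33% | 0.00 | −0.67 | −1.33 |
| same | Jan 2023 | 0% | −1.00 | −1.00 | −1.00 |
| 6 months, irregular, 3 visits a year | Jul 2022 | 52% | +0.16 | −0.52 | −1.20 |
| same | Jan 2023 | 19% | −0.51 | −0.80 | −1.09 |

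**Prevalence.** This outcome has no slope term. If care lowers prevalence by d among later screens, a 2023 rate that mixes both kinds of screen falls by about (1 − share) × d. At 49–68% that is 0.51d to 0.32d; at 0% it is the full d. The approximation counts scores, whereas the plan counts Veterans.

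**The case against.** A reader might infer that half or more of the *post* scores precede care and that a real reduction would be mostly hidden. The documents do not support that, for four reasons.

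- **The planned horizon is 12 months.** Section 5.7 ties the interaction to that point and says that effects can be estimated at different times. Under roughly annual screening the fitted effect at the end of 2023 keeps about 60–125% of the truth.
- **The share rests on missing inputs.** With one regular July–December visit a year and *post* from January 2023 there is no bias at all, because every trigger falls in 2022.
- **Some effect may come before a new screen.** Every cohort member visited during facilitation. Section 5.1 describes patient handouts and provider training that are not tied to a new screen, and care may follow an older positive screen. The calculation sets all this to zero. It also applies the effect to screen-negative Veterans, so absolute biases would shrink with the proportion positive, which is not given.
- **The question is clinic-level.** Section 5.7 concerns everyone seen during facilitation, with the site as its own control. It would be too strong to say that the plan cannot answer it.

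The plan also describes effectiveness as pilot data and a training opportunity.

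These points limit the size. They do not remove the double role of the first screen, make the indicator a valid reading of immediate change, or help the prevalence outcome. The slope would partly reflect when second screens fall due.

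**Conclusion.** The point holds in limited form. Followed as written, the analysis mixes triggering screens with follow-up scores. At 11–12 month screening, first screens are about 0–68% of 2023 scores, or about 50–86% of *post* scores if *post* starts in July 2022. At 6 months the corresponding figures are about 0–19% and 33–52% in the patterns examined.

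With irregular, roughly annual screening, the immediate-change term takes the wrong sign and the mid-period effect is diluted to about −0.2 to −0.4 of a true −1. The end-2023 effect largely survives, sometimes overstated. The reduction is thus mainly displaced from level to slope, and the 2023 prevalence is diluted.

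All sizes depend on an assumed interval, an assumed visit pattern and an assumed start of *post*. They are upper-end, because they allow no effect before the first new screen and a full effect on every later score. Severity: consider.

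**What to change.** **In section 5.7:**

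- Fix the date on which *post* starts and the time origin.
- Name the model-based effect at 12 months (indicator plus interaction times elapsed time) as the effectiveness estimate, in place of the indicator alone.
- Keep the calendar-date model, and add an analysis in which each Veteran's first AUDIT-C on or after July 1, 2022 is the index and only scores more than 30 days later count as outcomes.
- Compare these with index-to-next-screen pairs built the same way from earlier years, so that ordinary change between screens, including regression to the mean, is netted out. Use the same maximum follow-up and cut the pairs off before July 2022. Windows opening in July 2019 and July 2020 allow the full 18 months; one opening in July 2021 allows only 12, so it needs an equally shortened comparison or should be left out.

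**In section 5.1:** report the 2023 prevalence also among Veterans with a non-index 2023 AUDIT-C, with those Veterans as the denominator. Dropping index screens from the numerator alone would lower the rate mechanically.

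**In the results:** give the observed screening intervals and the number of Veterans with a second screen.

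**Cost:** wording, and recoding of dated scores already in the data pull. The added analysis uses fewer Veterans and favours those re-screened sooner. By 31 December 2023 a second screen would exist for roughly 13–37% of the cohort with irregular 11–12 month screening (about 1,300–3,700 of 10,000), 45–92% at 6 months, and about 94% with one regular visit a year. That is why it should sit beside the planned model and not replace it.

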## **5.2 Recruitment Methods**

Ann Arbor regulatory approval is being requested only for the data analysis portion of AIM 3 (extraction, cleaning, and analysis of AIM 3 outcome data from the VA's electronic health record via the Corporate Data Warehouse). All recruitment, enrollment and intervention activities were completed at the Pittsburgh VA.

Approximately 10,000 Veterans' data will be pulled from the CDW to examine implementation and clinical outcomes. Data to evaluate implementation and clinical effectiveness outcomes will be obtained electronically and securely from already collected administrative databases, using scrambled SSN or Patient ICN to link data together. Data sources will include the CDW, Health Factors (AUDIT-C and Brief Intervention information), Vital Status File to obtain DOB for calculating age of Veterans, and Prescription/Pharmacy information (for data on whether medications for alcohol use disorder were prescribed). Other specific records include: sociodemographics (e.g., sex, gender identity, marital status, indicator of socioeconomic status, race/ethnicity, sexual orientation), past-year diagnoses (Alcohol use disorder diagnosis, Substance use disorder diagnoses, Tobacco use disorder diagnosis, Mental Health disorder diagnosis (Depression, anxiety, PTSD, Bipolar, Psychotic-spectrum)), index of medical complexity (e.g., Charlson index, VA CAN score) utilization of primary care services pre-implementation (2019-2022), during (July 2022 - Dec. 2022) and post-implementation intervention (Jan 2023 - Dec. 2023), referral and utilization of substance use services in the past year (yes/no), and referral and utilization of past-year mental health services (yes/no). Data may also be reviewed within CAPRI/Joint Legacy Viewer (JLV) to allow study team members to look into potential data anomalies from our dataset. In addition, members of the study team may review notes, charts, dates of AUDIT-C administration, etc. to verify the accuracy of our Aim 3 dataset.

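### The Effectiveness time-series model accounts only for a linear pre-intervention trend, so a sustained shift in AUDIT-C during 2020–2021 could be read as a facilitation effect

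*Combined protocol and SAP*

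**What the plan says.** Section 5.7 models AUDIT-C scores for a single clinic, "where the intervention site will serve as its own control". The regressors are "an indicator for practice facilitation (pre- vs. post"), then "a continuous term for time (days since practice facilitation dissemination) and the interaction between the two". The level term is given a direct reading: "The indicator variable will assess immediate changes in AUDIT-C scores post implementation intervention". The interaction is read as a change in slope. One stated reason for choosing the method is that "historical trend is accounted for in the analytic model".

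The window is set in section 5.1: "The data pull will include data from January 1, 2019 – December 31, 2023". Section 5.7 gives no pre-period dates for the Effectiveness model. Dates appear for other purposes. For Adoption, section 5.1 has "Rates of alcohol-related care pre-intervention (2019-2022), during the course of the practice facilitation intervention (July 2022-December 2022"); for utilization data, section 5.2 has "pre-implementation (2019-2022), during (July 2022 - Dec. 2022) and post-implementation intervention (Jan 2023 - Dec. 2023"). Both labels put July–December 2022 in the pre-period and the active period at once, and neither says on which side of the Effectiveness indicator those months fall.

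The plan has no comparison series, non-linear or calendar-period term, or sensitivity analysis for this model. It does not mention the pandemic and reports no past AUDIT-C values.

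**The concern.** With the interaction included, the model fits a separate straight line in each phase. The pre-period line, extended forward, is the only counterfactual. Anything in the earlier history that is not linear is forced into that line's height and slope, and no second site can absorb the error.

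If the pre-period starts in January 2019, it covers 2020 and 2021, when a temporary change in drinking, visits or screening is plausible. An upward shift would lift the counterfactual and make facilitation look beneficial when it did nothing. A downward shift would make it look harmful or hide a benefit. The assurance in section 5.7 invites readers to think that this risk has been handled.

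**Working it through.** The plan gives no SD, alpha, effect size or screening frequency for this analysis, so there is no figure of its own to reproduce. The check asks what the section 5.7 model returns when the true effect is zero and the series contains a bump of size b.

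**Inputs from the documents:** January 2019–December 2023 (60 months); active phase July–December 2022; model terms as in section 5.7; about 10,000 Veterans (section 5.2).

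**Assumed:** a bump from April 2020 to June 2021 (15 months), equal monthly volume, 10,000 independent scores a year (833.3 a month), SD 2.5, two-sided 5% test.

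**Bias.** The post-period line is fitted separately and is flat at zero, so the level bias is minus the pre-period line's value at the break. Time is in years at month midpoints, and Sxx = n(n² − 1)/(12 × 144) for n pre-period months.

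1. *Break July 2022.* n = 42, mean time −1.75, Sxx = 42 × 1763/1728 = 42.85. The bump has mean time −1.625.
   - Mean height: 15/42 = 0.357b.
   - Slope: 15 × 0.125/42.85 = 0.044b per year.
   - Line at the break: 0.357 + 0.044 × 1.75 = 0.434, so the level bias is **−0.43b**.
   - At the end of 2023: 0.357 + 0.0438 × 3.25 = 0.499, so that contrast is biased by −0.50b.
2. *July–December 2022 counted as pre.* n = 48, mean time −2.0 from January 2023, Sxx = 48 × 2303/1728 = 63.97, bump mean −2.125.
   - Slope: 15 × (−0.125)/63.97 = −0.029b per year.
   - Level bias: −(0.3125 − 0.0293 × 2) = **−0.25b**.
3. *July–December 2022 excluded.* The line from case 1 is extended to January 2023: 0.357 + 0.0438 × 2.25 = 0.456, so the bias is **−0.46b**.

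**False rejection of the level test at b = 0.2.** The SE is the square root of (2.5²/833.3) × [1/n + d²/Sxx, summed over both phases], where d is the distance from each phase's mean time to the break.

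| Coding | Bracket | SE | z = 0.2 × bias/SE | Rejects |
|---|---|---|---|---|
| Break July 2022 | 0.0953 + 0.2227 | 0.049 | 1.78 | 43% |
| Counted as pre | 0.0834 + 0.3351 | 0.056 | 0.91 | 15% |
| Excluded | 0.1420 + 0.3351 | 0.060 | 1.52 | 33% |

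**Range, break July 2022.**
- At b = 0.1, z halves to 0.89 and rejection is about 14%.
- At b = 0.2, SD 3 gives z = 1.48 (32%) and SD 2 gives z = 2.22 (60%).
- Six-month bump (April–September 2020): mean height 6/42 = 0.143b, slope 6 × (−0.25)/42.85 = −0.035b, level bias −0.08b, rejection about 6% at b = 0.2.
- Bump ending December 2020: −0.17b. Ending March 2022: −1.06b.

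**Slope change.** The 15-month bump is nearly centred in the pre-period, so the slope bias is only −0.04b per year and the slope test rejects about 5% at b = 0.2. A shift from April 2020 that lasts through June 2022 gives 27 × 0.625/42.85 = 0.39, a bias of −0.39b per year. With SE 0.049, z = 0.2 × 0.394/0.049 = 1.61 and rejection is about 36%.

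**Can one fixed remedy be trusted?** With a July 2022 break, an April 2020–June 2021 indicator removes the bias entirely if those dates are right and moves the level SE only from 0.049 to 0.050. If the bump ran to December 2021, it leaves −0.50b on level and −0.72b at end-2023, while a pre-period restricted to July 2021–June 2022 gives +0.26b and +2.52b. If the bump ran to March 2022, the level biases are −0.79b and −0.18b: same sign, both wrong.

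**The case against.** The strongest objection is that the bump is hypothetical. The documents give no AUDIT-C history, so its existence, sign, size and length are all assumed. That stands. A reader might infer that the pandemic will produce a false effect here; the documents support only that the model could not separate one.

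A reader might also take the pre-period to be January 2019 to mid-2022. Section 5.7 does not say so, and the coding of July–December 2022 moves the level bias from −0.43b to −0.25b. The bias shrinks but keeps its sign under all three codings.

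A third tempting reading is that the bump tilts the line and so distorts both the level and the slope term. For a bump of about a year it mainly raises the line; slope distortion needs a longer or lasting shift.

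Section 5.7 sets no significance threshold, so the rejection rates describe a test that the plan does not name. They show scale only and ignore autocorrelation and repeated scores per Veteran.

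Finally, the plan calls a measurable clinical impact unlikely and treats effectiveness as pilot data and training, and it notes that results can be graphed. This limits the weight of the point. It does not remove it: the estimates are meant to inform a larger trial, and the plan does not say what to conclude if a plot shows a non-linear history.

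**Conclusion.** The concern holds in a conditional form. The claim about historical trend is too broad, because the model handles a linear trend and nothing else. Given a pre-period from January 2019, a shift lasting about a year or more in 2020–2021 can create a false level change: −0.25b to −0.46b for the 15-month example, with 15% to 43% false rejection at b = 0.2 under the stated assumptions. A false slope change of note requires a shift that persisted. A six-month shift does little, and a downward one reverses every sign. The documents cannot tell which case applies, which is the reason to prespecify checks and not to assume a bias in either direction. For a pilot this is a worthwhile and inexpensive correction, not a flaw that invalidates the study.

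**What to change.** In section 5.7:

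- Replace "historical trend is accounted for in the analytic model" with wording such as *a linear pre-intervention trend is accounted for*.
- State where the Effectiveness pre-period starts and how July–December 2022 is coded, since the checks below depend on both.
- Prespecify sensitivity analyses on the data already being pulled: (a) the same model with a pandemic-phase term, with the phase dates varied; (b) the pre-period restricted to a later start.
- Commit to plotting the full series.
- Attribute a level or slope change to facilitation only if it is robust across these analyses; otherwise report it as inconclusive pilot data. Agreement in sign between two runs is not enough, as the March 2022 example shows.

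The cost is a few extra model runs and no new data. The restricted window is much less precise: with a July 2021 start the end-2023 SE is about 0.18 against 0.06. At that SE a true 0.1-point reduction would show the wrong sign about 29% of the time (0.1/0.18 = 0.56 SE), so this run should inform judgement and not act as a veto. Bias remains if the phase dates are wrong. A concurrent comparison clinic would be stronger but would need a further data pull.

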#### **5.4 Inclusion/Exclusion Criteria**

We will include all Veterans with a visit to the Pittsburgh VA primary care during the practice facilitation intervention.

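### The Effectiveness model has no case-mix adjustment, so a change in which Veterans are scored that coincides with the intervention would be confounded with the level or slope effect on AUDIT-C

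*Combined protocol and SAP*

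**What the plan says.** Section 5.7 (Data Analysis) describes the Effectiveness analysis as a time series in which "the intervention site will serve as its own control". The AUDIT-C score is to be "modeled using a regression model with an indicator for practice facilitation (pre- vs. post-), a continuous term for time", with time counted as "days since practice facilitation dissemination) and the interaction between the two". The list of terms ends there. No covariate, patient-level term or sensitivity analysis is given for this model. The reason for the design is stated: "Time-series analysis was chosen because historical trend is accounted for in the analytic model".

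The population is in section 5.4: "We will include all Veterans with a visit to the Pittsburgh VA primary care during the practice facilitation intervention". Section 5.1 dates the intervention to July–December 2022 and the data pull to January 2019–December 2023.

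Section 5.2 lists variables that could describe case mix: "Vital Status File to obtain DOB for calculating age of Veterans", sex, race/ethnicity and other sociodemographics, "past-year diagnoses (Alcohol use disorder diagnosis, Substance use disorder diagnoses" and others, and "index of medical complexity (e.g., Charlson index, VA CAN score" and similar). The subgroup Reach denominators in section 5.1 would draw on sex and race/ethnicity. No section assigns any of these variables to the Effectiveness model.

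**The concern.** An AUDIT-C score exists only when a Veteran is screened. The cohort rule selects on a visit in July–December 2022, not on having scores in both periods. Two routes to a compositional change follow:

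- A Veteran whose first visit falls in the intervention window may have no score from 2019 to mid-2022 and so contribute only afterwards.
- A Veteran who dies, leaves or is not rescreened contributes only beforehand. Facilitation worked on how the clinic handles unhealthy alcohol use, so it could itself change who is rescreened.

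Either change can fall at the date where the model looks for its effect. With no concurrent control, the model has only its time terms to separate a change in drinking from a change in who is measured. The estimate is meant to inform a larger trial, so a confounded value could mislead that planning.

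**Working it through.** The plan gives no SD, effect size, alpha or screening count for this outcome, so there is no planned figure to reproduce. The check fits the stated model (level, time, level × time) with a true effect of zero and an assumed change in case mix.

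**Inputs.** From the documents: 60 months of data (January 2019–December 2023), facilitation starting July 2022, about 10,000 Veterans. Assumed: break at 1 July 2022 (42 months before, 18 after); a subgroup scoring D = 3 to 4 points higher, such as Veterans with an AUD diagnosis; its share among scored Veterans rising by s = 0.02 (8% to 10%) or 0.04 (8% to 12%).

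**Noise-free fit, by shape of the shift.**

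| Shape of the change in share | False level change | False slope change per year |
|---|---|---|
| Linear over 2019–2023 | 0.000 | 0.000 |
| Step at the break | D × s | 0.000 |
| Drift starting at the break | 0.000 | D × s / 1.5 |

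- Step: 3 × 0.02 = 0.06; 4 × 0.02 = 0.08; 3 × 0.04 = 0.12; 4 × 0.04 = 0.16 points.
- Drift from the break (18 months = 1.5 years): 0.06 / 1.5 = 0.04 up to 0.16 / 1.5 = 0.11 points per year.
- With smaller gaps (D = 0.5 to 2, s = 0.02 to 0.10) a step gives 0.5 × 0.02 = 0.01 up to 2 × 0.10 = 0.20.

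**Against sampling error.** Assume SD 2.5 and 833 scores a month (10,000 / 12), treated as independent. The variance of a monthly mean is 2.5² / 833 = 0.0075. The SE of the level term then depends on the window:

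| Window | Level SE | Step bias 0.06 to 0.16, in SEs |
|---|---|---|
| Break July 2022, all later months post | 0.049 | 1.2 to 3.3 |
| Break January 2023 | 0.056 | 1.1 to 2.9 |
| Only 2023 as post, level read at July 2022 | 0.094 | 0.6 to 1.7 |

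These SEs ignore repeated scores within a Veteran, so the multiples are only indicative.

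**Fixed-cohort simulation.** 10,000 Veterans, roughly annual scores, an assumed 1-point gap between two strata, true effect zero, patient-clustered errors, 60 replicates per scenario. Adjustment is for one binary covariate.

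| Scenario | Level, unadjusted | Level, adjusted | Rejection at 5%, unadjusted / adjusted |
|---|---|---|---|
| No new entrants, equal screening | 0.000 | 0.007 | 0.03 / 0.03 |
| 10% new entrants with a different mix | 0.030 | 0.009 | 0.15 / 0.10 |
| 20% new entrants with a different mix | 0.043 | 0.004 | 0.22 / 0.03 |
| Post-period screening 60% high, 80% low stratum | −0.057 | −0.002 | 0.35 / 0.08 |
| 10% new entrants; screening 90% high, 70% low | 0.084 | 0.003 | 0.53 / 0.07 |

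With 60 replicates the rejection rates are imprecise. Bias appears only when new entrants differ or screening becomes differential, and a measured covariate that captures the difference removes most of it.

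**The case against.** The strongest reply is that the design already limits the problem. The model carries the pre-period trend, and the fit above confirms that steady linear drift leaves no false level or slope change. The population is one cohort, not separate before and after samples; with no new entrants and equal screening the simulated bias is zero. A reader might infer that any difference between earlier and later scored Veterans will be read as a change in drinking, or that case mix is known to differ. The documents do not support either: they give no screening counts and no case-mix figures, and only a shift that coincides with or begins at the intervention does the main damage. A temporary pre-period shift leaks through in smaller amount.

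A reader might also take a bias of 1 to 3 standard errors as established. It is not. It needs an abrupt step, assumed inputs throughout and a favourable window; under another reading of the post period it is 0.6 to 1.7.

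It is also fair that measured covariates cannot cure unmeasured selection, and that a diagnosis recorded just before July 2022 may be a consequence of a high AUDIT-C in 2019–2021, so it is not a clean baseline for those scores. Finally, sections 5.1 and 5.7 present Effectiveness as pilot and training work in which a measurable effect is not expected.

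What these replies leave standing is the gap itself. One cohort does not mean one set of scored Veterans in both periods, and a linear time term does not remove a break in composition at the intervention date.

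**Conclusion.** The point holds in conditional form. The model is stated without case-mix adjustment, relevant variables are already being pulled, and the cohort rule leaves room for the mix of scored Veterans to change at or after the intervention. Such a change would be confounded with the level or slope term. Whether it occurs, and how large it is, cannot be derived from the documents. Under the assumed inputs the false level change for a step is the score gap times the change in share, 0.06 to 0.16 points in the main example and 0.01 to 0.20 across the wider range; it is zero for linear drift. Because the outcome is exploratory and no stated decision rule depends on it, this is a worthwhile low-cost improvement, not a flaw that undermines the study.

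**What to change.** In section 5.7, amend the Effectiveness model as follows.

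1. Add age, sex, race/ethnicity, Charlson or CAN score, and mental health and substance use diagnoses, at pre-intervention values. Use no value recorded after facilitation began, since facilitation could change it.
2. Take AUD diagnosis from the start of each Veteran's record, or add it only in a sensitivity analysis, because one recorded shortly before July 2022 may follow from earlier AUDIT-C scores.
3. Add a Veteran random intercept with cluster-robust standard errors for repeated scores.
4. Report two sensitivity analyses: the unadjusted model, and a model restricted to Veterans with scores on both sides of the intervention.

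Cost: a few sentences, a little more analysis and no new data fields. New entrants without pre-intervention records need a missing-value code, which is only a partial remedy for them. The random intercept alone is not enough, because Veterans scored on one side only still carry case-mix differences into the estimate. Unmeasured selection into screening remains and should be stated as a limitation.
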